3.2.1 Stage 1 Design

In Stage 1 of the trial, we will randomize approximately 200 primary care providers at Atrius Health approximately equally to either usual care or active intervention. Of the half of providers randomized to active intervention, we will randomize them equally to one of 15 active intervention arms. Providers randomized to one of the 15 active intervention arms will receive an EHR tool to guide the care of their eligible patients. Providers randomized to usual care will receive no EHR tool, as is current clinical practice. Providers will be eligible for the trial if they prescribed a

benzodiazepine or sedative hypnotic to at least one older adult in the 180 days prior to randomization. We will randomize providers within strata based on their clinic size and baseline rates of high-risk medication prescribing.

Eligible patients of these providers will be who meet the following criteria: 1) older adults (aged 65 years or more) and 2) who have been prescribed at least 90 pills of benzodiazepine or sedative hypnotic in the last 180 days.

After 6 months (dictated by the average number of observed data points, i.e., at least 1 eligible patient for whom the EHR tools fired per physician), an interim analysis of Stage 1 participants will be performed to rank the 15 active intervention arms based on their observed effect size at reducing prescribing of high-risk medications. Up to 5 of the most promising active intervention arms based on their effect size will be tested in Stage 2. If more than 5 are promising, we will choose the top 5. If 1 to 5 arms are promising, we will choose those for testing in Stage 2. If none are promising, we will combine active interventions within the arms based on the most effective factors. After this interim analysis, the Stage 1 providers in the “winning” arms (i.e., the promising arms) will be randomly assigned to continue to receive their original treatment assignments or to usual care to test holdover/persistency effects. Similarly, the Stage 1 providers assigned to treatment arms determined to be statistically inferior will be randomly assigned in equal proportions to one of the winning arms or to usual care.

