3.2.2 Stage 2 Design

In Stage 2, we will randomize the primary care providers at Atrius Health who were assigned to usual care in Stage 1 in equal proportions to up to one of the 5 most promising treatment arms or to continue to receive usual care. We will also randomize any additional providers who prescribed at least one eligible anticholinergic to at least one older adult in the 180 days prior to randomization for secondary analyses. Providers randomized to one of the 5 selected treatment arms will receive an EHR tool to guide their care of eligible patients. As in Stage 1, we will randomize providers based on demographic characteristics, patient case-mix factors, and

baseline rates of high-risk medication prescribing. Patient eligibility will be identical to that used in Stage 1 except patients will also be included if they had been prescribed at least 90 pills of eligible anticholinergics in the last 180 days. Follow-up in Stage 2 will last at least 8 months, until enough data points have accrued.

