3.2.3 Replication Trial Design

[figure not shown]
This replication trial is a cluster-randomized, NIH-defined Phase III pragmatic trial. The study statistician, in partnership with data analysts at MGB, will generate and implement the randomization scheme, with oversight by the Principal Investigators. All the study sites will be at MGH for this trial; we have received approval from leadership at MGH primary care practices and Digital Health eCare teams to conduct this trial. For study evaluation, data regarding patients' medical history, disease control, medication use, and healthcare utilization will be obtained from EHR data or administrative claims data. The administrative claims data used for evaluation in this study will come directly from MGB in HIPAA-limited datasets through their risk-bearing contracts, as applicable.

We plan to randomize primary care providers at MGH to one of the 2 most promising treatment arms identified in the adaptive randomized trial conducted at Atrius Health or usual care. We expect to randomize approximately 200 providers. Providers randomized to one of the 2 selected treatment arms will receive an EHR tool to guide their care of eligible patients. If the adaptive trial does not demonstrate the superiority of any EHR tools over usual care, we will select the two statistically most promising of the arms for this parallel group trial. We will randomize providers based on provider demographic characteristics, patient case-mix factors, and baseline rates of high-risk medication prescribing measured in EHR data.

[figure not shown]
Providers will be eligible if they prescribed a benzodiazepine, sedative hypnotic, or two distinct anticholinergics to at least one older adult in the 180 days prior to randomization. Providers will receive these EHR tools for their patients who meet the following criteria: 1) older adults (aged 65 years or more), and 2) who have been prescribed at least 90 pills of benzodiazepine or sedative hypnotic or have been prescribed at least one active orders of at least 90 pills of two different anticholinergics in the last 180 days. Follow-up will last 12 months. These patients will also be included in the analyses. The type and timing of EHR tool that the providers receive for these patients will vary based on their assigned intervention arm.

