5.3 Measures to minimize bias: randomization and blinding

Providers will be randomized to treatment arms in equal proportions based on blocks. We will use provider-based cluster randomization to minimize the possibility of contamination in study interventions between practices and clinic staff. For the randomization, we will use stratified randomization based on clinic practice size and baseline rates of prescribing to reduce potential imbalances between the providers assigned to the treatment arms.

The providers will not be blinded to which arm they were assigned to, as blinding is the context of an intervention that is intended to motivate action will be infeasible. The study statistician, in partnership with data analysts at Atrius Health, will generate and implement the randomization scheme, with oversight by the Principal Investigators. Investigators will be blinded to the treatment arms during interim and final analyses.

6. Study Assessments and Procedures

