6.1 Baseline data

We will collect baseline data on patients and providers using extracted EHR data and/or administrative claims data as applicable for the study aim. This baseline data will be used to assess any potential imbalances in the characteristics of providers or patients despite randomization. The baseline data will include, but are not limited to: gender, rural/urban practice setting, baseline rates of prescribing, practice location, and patient case-mix. We will also collect patient data that include but are not limited to: sociodemographic data, medical history and comorbidities, baseline resource utilization in prior 12 months (i.e., number of visits), biometric values (e.g., serum creatinine, systolic/diastolic blood pressures).

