7.3 Statistical analyses

7.3.1 *Analysis of the primary endpoints*

7.3.1a Adaptive trial

The unit of analysis is at the patient-level. Therefore, for the primary outcome, we will use a generalized linear mixed model for binary outcomes to adjust for physician-level

clustering and multiple patient observations per physician. The study arms will be analyzed using a multivariable regression model, in which each of features of the EHR tools (“factors”) will be included as covariates in an overall regression model that compares the effect of receiving an enhanced EHR decision support tool compared with usual care. In specific, these factors will include: timing of EHR tool (open encounter=1, order entry=0), whether a follow-up alert is enabled as part of the tool (yes=1, no=0), cold state outreach is used (yes=1, no=0), simplification is used (yes=1, no=0), sign-off is used (yes=1, no=0), pre-commitment is used (yes=1, no=0) or if different risks of the high-risk medications are presented within the EHR tool (yes=1, no=0). In this way, we will also observe and report an overall effect of the enhanced EHR tool compared with usual care as well as the effect of individual features through their coefficients in the model. We will conduct this interim analysis once at the end of follow-up in Stage 1 to determine the arms with the most potential promise. In specific, the 15 active arms will be ranked based on their observed effect size at reducing prescribing of high-risk medications from the covariate coefficients from the models. At the end of follow-up in Stage 1, we will also use these regression models to explore whether any of the intervention arms (defined by factors) are inferior to usual care. We will repeat these analyses at the end of Stage 2 using all available data to determine whether any of the intervention factors (and secondarily, arms) were more effective than usual care at reducing prescribing of high-risk medications. In secondary analyses, we will include anticholinergics.

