Because this is a randomized trial, our primary analyses are planned as unadjusted; in secondary analyses, we will adjust for patient age, race/ethnicity, and gender.. Given the nature of the data and how the outcomes are categorized, there will not be missing values for the primary endpoint, as the absence of action is classified as no action by the provider. For the primary analysis, we will include all eligible patients in the denominator who had at least one in-person or telehealth visit with their primary care provider. In secondary analyses, we will

include all eligible patients of those primary care providers in the denominator, regardless of whether the patient visited the provider over the follow-up period.

7.3.1b Replication trial

All analyses will use intention-to-treat principles. We will use generalized estimating equations to adjust for clustering and repeated observations. For the inappropriate prescribing outcome, we will use a log link function and binary distributed errors. For the adverse clinical outcomes, we will use a log link function and binary distributed errors. These models generate the estimated relative risks (RRs) with robust standard errors and are considered to be particularly appropriate when outcomes are common (e.g., incidences of $\geq 10\%$). Because this is a randomized trial, our primary analyses are planned as unadjusted; however, in secondary analyses, we will adjust for patient age, race/ethnicity, and gender.

Given the nature of the data and how the outcomes are categorized, there will not be missing values for the primary endpoint, as the absence of action is classified as no action by the provider. For the primary analysis, we will include all eligible patients in the denominator who had at least one visit with their primary care provider. In secondary analyses, we will include all eligible patients of those primary care providers in the denominator, regardless of whether the patient visited the provider over the follow-up period.

7.3.2 *Analysis of secondary endpoints*

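### Provider baseline prescribing rate is used to randomise but appears in no named model, so the unadjusted primary tests are valid but conservative if the rate is balanced by design and predicts outcome

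*Combined protocol and SAP*

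**What the plan says.** **Randomisation.** For Stage 1, section 3.2.1 states: "We will randomize providers within strata based on their clinic size and baseline rates of high-risk medication prescribing". Section 5.3 agrees, describing "stratified randomization based on clinic practice size and baseline rates of prescribing". For Stage 2, section 3.2.2 says "As in Stage 1, we will randomize providers based on demographic characteristics, patient case-mix factors, and" baseline prescribing rates. For the replication trial, section 3.2.3 says: "We will randomize providers based on provider demographic characteristics, patient case-mix factors, and baseline rates of high-risk medication prescribing measured in EHR data". Baseline prescribing is common to all four. The other factors are not: clinic size in 3.2.1 and 5.3, demographics and case-mix in 3.2.2 and 3.2.3. After the interim analysis, Stage 1 providers in the winning arms "will be randomly assigned to continue to receive their original treatment assignments or to usual care to test holdover/persistency effects". No factors are named for that step.

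**Data.** Section 6.1 collects the rate in order to look for imbalance: "The baseline data will include, but are not limited to: gender, rural/urban practice setting, baseline rates of prescribing, practice location, and patient case-mix".

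**Models.** Sections 7.3.1a and 7.3.1b both state: "Because this is a randomized trial, our primary analyses are planned as unadjusted". The primary models therefore carry no baseline covariates; secondary models add patient age, race/ethnicity and gender. The adaptive analysis is later pooled: "We will repeat these analyses at the end of Stage 2 using all available data". Section 7.3.2 lets patient-level predictors enter the primary model if they are judged strong and out of balance, but defines neither term. Section 7.3.5 gives open-ended examples for secondary models. Practice size is among them; the baseline prescribing rate is not.

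**The concern.** When randomisation forces arms to be alike on a factor that predicts outcome, the treatment estimate varies less from one randomisation to the next. A model that omits the factor does not see this: it leaves the factor's variation in the residual and reports a standard error that is too large. Intervals are then too wide and the test rejects too rarely. The information needed is already in hand, so any precision lost is lost for nothing.

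For the replication trial, the question is whether this touches the power statement in 7.2. For the secondary and tertiary endpoints there is a separate problem. Without a list or threshold in 7.3.2, two analysts could fit different primary models to the same endpoint. The rate itself cannot enter by that route, because the trigger admits only patient-level predictors.

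**Working it through.** **Inputs from the documents.** Section 7.2: replication intra-provider correlation 0.1, a 10-point difference, power above 80%, Holm-Bonferroni; adaptive correlation 0.3, control rate 5%, odds ratio 1.15, 20 patients per provider. Section 3.2.3: about 200 providers and three arms, so about 67 per arm.

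**Assumed.** The share R² of between-provider variance explained by the strata: 0, 10, 25, 50%. Replication patients per provider m: 10 or 20, since 7.2 gives none for that trial. The adaptive trial uses 20; section 4.3.2 implies 2000/201, about 10, for Stage 1. Replication control rates: 5 to 40%, since none is stated.

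**1. Variance.** On the cluster-mean scale v = ρ + (1−ρ)/m, and the reduction from adjusting is ρR²/v.
- m = 20: v = 0.1 + 0.9/20 = 0.145. At R² = 25%, 0.1 × 0.25/0.145 = 0.172. Across R²: 0/7/17/34%.
- m = 10: v = 0.190. Across R²: 0/5/13/26%.

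**2. True size of the unadjusted test**, with arms balanced within strata: 2[1 − Φ(1.96/√(1 − reduction))]. At m = 20 and R² = 25%: 1.96/√0.828 = 2.154, which gives 3.1%. Across R²: 5.0/4.2/3.1/1.5%.

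Simulation of a log-link GEE with robust standard errors (four blocked strata, control rate 30%, m = 20) gives 4.9/4.3/3.5/1.7% unadjusted and 4.9 to 5.4% adjusted. A second simulation, at control rate 20% and R² of 0/30/50/80%, gives 5.4/3.3/2.2/0.9% unadjusted and 4.9 to 5.3% adjusted. Under simple randomisation the unadjusted test stays near 5%, so the conservatism comes from the design balance.

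**3. The plan's own power figure.** The figure of more than 80% cannot be strictly reproduced without a cluster size and control rate. Over the assumed range, SE = √{[p₀(1−p₀) + p₁(1−p₁)]v/66.7} with p₁ = p₀ + 0.10. At p₀ = 30% and m = 10: √(0.45 × 0.19/66.7) = 0.0358.

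Under Holm, power for one comparison is P(Z₁ > 2.241) + P(1.960 < Z₁ ≤ 2.241 and Z₂ > 2.241). Z₁ and Z₂ are correlated through the shared control arm; at p₀ = 30% the correlation is 0.21/0.45 = 0.47. Unadjusted, each Z has mean 0.10/SE and SD √(1 − reduction). Adjusted, it has mean 0.10/[SE√(1 − reduction)] and SD 1.

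With both arms truly 10 points better:
- m = 20, unadjusted, R² = 0: about 99.9, 99, 93, 87 and 84% at control rates of 5, 10, 20, 30 and 40%.
- m = 10, across R² (good to about one point):

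| Control rate | Unadjusted | Adjusted |
|---|---|---|
| 30% | 76/77/78/80% | 76/79/82/88% |
| 40% | 72/73/74/76% | 72/75/79/86% |

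At a fixed 0.025 level, the 30% row becomes 71/71/72/74% against 71/74/78/84%, and the 40% row 67/67/68/69% against 67/69/74/81%.

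**4. Adaptive trial, pooled enhanced arms against usual care.** Odds 0.05/0.95 × 1.15 give 5.71%. Fourteen of 15 active arms hold about 93 of 100 active providers. With v = 0.335 at m = 20, SE = √[(0.0475/100 + 0.0538/93) × 0.335] = 0.0188, so the difference is 0.0071/0.0188 = 0.38 standard errors. Adjusted power is 6.6% at R² = 0 and 8.0% at R² = 50%; at m = 10 it is 6.5 to 7.5%.

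**5. Quantity prescribed.** Adjusting for a patient's baseline quantity leaves a variance ratio of 1 − r². For assumed correlations of 0/0.3/0.5/0.7 the cut is 0/9/25/49%.

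**The case against.** An unadjusted primary analysis, pre-specified with adjusted secondary models, is legitimate. All analysed patients already meet a pill-count threshold, the outcome is stopping or tapering, and nothing in the documents says a provider's prescribing rate predicts it. If R² is zero, nothing is gained. Conservatism also needs balance by design. Sections 3.2.1 and 5.3 state strata, but 3.2.2 and 3.2.3 say only that randomisation is based on the factors. All of this stands, and it makes the benefit conditional.

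A reader might infer that the unadjusted tests are biased or reject too often. They are not and do not; any error runs toward too few rejections. A reader might also infer that the replication trial misses its stated power without adjustment. The documents do not support that: they give neither cluster size nor control rate, and Holm is less demanding than a fixed 0.025 level when both arms work. If only one arm works, less of the Holm gain is realised and power moves toward the fixed-level figures.

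Finally, 7.3.2 follows patients until they leave Atrius, so it can be read as adaptive-trial text, with 7.3.1b governing the replication adverse outcomes. That is a fair reading, so the overlap is an ambiguity and not a proven contradiction.

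**Conclusion.** The point holds as a missed, nearly free gain in precision and not as a flaw in validity. The textual part is firm: the rate is a randomisation factor wherever factors are named, it is collected, and no named model uses it. Section 7.3.5 is open-ended and could admit it later, but only in a secondary analysis.

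The size depends on R², which is unknown, and on the rate being balanced by design. Under Holm with both arms effective, adjustment changes whether 80% is exceeded only at about 10 patients per provider, control rates of 30% or more, and R² of roughly 25 to 50%. With 20 patients per provider, unadjusted power is already about 84% or more up to a 40% control rate. The adaptive trial's power stays below 10% with or without adjustment.

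The undefined trigger and the conflicting factor lists are secondary, but they need correcting whatever R² is.

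**What to change.** - In 7.3.1a, 7.3.1b and 7.3.2, pre-specify the provider baseline prescribing rate, in the categories used for randomisation, as a fixed effect in the primary models, with any other factor actually used to stratify. In the pooled Stage 1 and 2 model, use the rate measured before the provider's first randomisation, so that Stage 1 exposure cannot affect it.
- For quantity prescribed, add the patient's milligram equivalents from EHR orders in the 180 days before randomisation, in the replication trial and in single-stage analyses. In a pooled model, pre-specify how to handle patients who become eligible only in Stage 2, whose earlier values may be stale or absent.
- Name a fallback if the log-binomial model does not converge, such as modified Poisson GEE with robust standard errors. One four-level factor gave no failures in 2,200 simulated fits at outcome rates of 30 to 60%, but several factors together, or uncommon outcomes, are untested.
- Keep the unadjusted model as a sensitivity analysis, and state that the adaptive odds ratio is then conditional on the strata.
- Secondarily, replace the 7.3.2 trigger with this fixed list, state whether 7.3.2 or 7.3.1b governs the replication adverse clinical outcomes, and reconcile the factor lists in 3.2.1 and 5.3 with those in 3.2.2 and 3.2.3.

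The cost is SAP wording, minor programming, and deriving baseline milligram equivalents, because eligibility counts pills. The downsides are a conditional odds ratio in the adaptive trial and no gain if the rate does not predict outcome.

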4.1 Inclusion Criteria

The study will include provider and patient subjects. Limited inclusion criteria will be applied to maximize generalizability in accordance with pragmatic trial principles by PRECIS-2 (PRagmatic Explanatory Continuum Indicator Summary).²⁸ The study criteria are defined below.

Stage 1

Providers will be eligible for this Stage of the trial if they:

- are a primary care provider at Atrius Health
- prescribed a benzodiazepine or sedative hypnotic to at least one older adult (aged 65 years or more) in the prior 180 days

Patients will be included for this Stage of the trial if they:

- are the primary care patient of an eligible provider
- are aged 65 years or more
- have been prescribed at least 90 pills of benzodiazepine or sedative hypnotic in the prior 180 days

Stage 2

Providers will be eligible for this Stage of the trial if they:

- are a primary care provider at Atrius Health
- prescribed a benzodiazepine, sedative hypnotic, or anticholinergic to at least one older adult in the 180 days prior to randomization

Patients will be included for this Stage of the trial if they:

- are the primary care patient of an eligible provider
- are aged 65 years or more
- have been prescribed at least 90 pills of benzodiazepine or sedative hypnotic or at least 90 pills of an eligible anticholinergic in the prior 180 days

Replication

The subjects involved in this trial are providers from multiple clinical sites, all at Mass General Hospital. The target population of providers and the patients they treat is pragmatic and widely representative. Providers will be eligible if they treat older adult patients. Each study clinic has an EHR system in place. The inclusion criteria are limited to maximize generalizability in accordance with pragmatic trial principles by PRECIS-2 (PRagmatic Explanatory Continuum Indicator Summary).

Providers will be eligible if they:

- Are a primary care provider at Mass General Hospital, with a minimum clinical schedule of 2 sessions per week
- Prescribed a benzodiazepine, sedative hypnotic, or anticholinergic to at least one older adult in the 180 days prior to randomization

Patients will be included if they:

- Are assigned to one of the randomized primary care providers (by MGB indicators)
- Are aged 65 years or more

- Have been prescribed at least 90 pills of benzodiazepine or sedative hypnotic or at least one active orders of at least 90 pills of two different anticholinergics in the prior 180 days

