6.2 Outcomes

For both Stages, the primary outcome will be a binary composite measure of a reduction in inappropriate prescribing, evaluated using EHR data from Atrius Health. In specific, we will measure a composite of 1) discontinuation of high-risk medications (benzodiazepines, sedative hypnotics, or anticholinergics [included in secondary analyses]), defined by either: a) active discontinuation and no subsequent order or b) no order during follow-up or 2) ordering a gradual dose taper (for benzodiazepine or sedative hypnotics). If either of these actions is taken by the provider for a specific patient at any point in the follow-up window, we will classify the patient as having had a reduction in inappropriate prescribing. If the patient has multiple therapeutic classes of interest (e.g., benzodiazepines and sedative hypnotics), we will classify patients with a reduction for any class as a “reduction” for the composite measure. In secondary analyses, we will include anticholinergics. We will also stratify patients by their number of eligible therapeutic classes (i.e., one, two, or three classes) and analyze outcomes within these strata.

In Stage 2 and the replication trial, secondary outcomes include the quantity of high-risk medication prescribed, defined by number of milligram equivalents of high-risk medications prescribed to patients in the follow-up period to capture cumulative prescribing by all providers

at Atrius Health. As above, we will also stratify patients by their number of eligible therapeutic classes (i.e., one, two, or three classes) and analyze outcomes within these strata.

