For the secondary outcome of cumulative medication prescribing, will use an identity link function and normally distributed errors within the generalized linear models. For tertiary adverse clinical outcomes and resource utilization outcomes, we will use a log link function and binary distributed errors within the overall multivariable models. These models generate the estimated relative risks (RRs) with robust standard errors and are considered to be particularly appropriate when outcomes are common (e.g., incidences of $\geq 10\%$). For these outcomes from claims data, we will follow patients whose providers are randomized to the study from the time

of randomization until they are censored due to loss of continuous enrollment in their health plan or leaving Atrius Health. Due to the nature of the randomization, we do not anticipate any systematic differences in the amount of follow-up time per arm but will account for any imbalances using inverse probability censoring weights.

Because this is a randomized trial, our primary analyses are planned as unadjusted; however, if there are strong patient-level predictors of the outcomes not balanced by stratified randomization, we will adjust for these in the primary analyses. Given the nature of the data and how the outcomes are being measured, there should not be missing values. However, should there be sufficient missing data (e.g., >10%), we will use multiple imputation.³¹

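### The main analysis of cumulative milligram equivalents should prespecify each patient's baseline quantity as a covariate, instead of adjusting only where imbalance is seen

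*Combined protocol and SAP*

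**What the plan says.** Section 6.2 defines the secondary outcome for Stage 2 and the replication trial as the "number of milligram equivalents of high-risk medications prescribed to patients in the follow-up period". For this outcome, Section 7.3.2 "will use an identity link function and normally distributed errors within the generalized linear models".

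On adjustment, the same section says: "Because this is a randomized trial, our primary analyses are planned as unadjusted; however, if there are strong patient-level predictors of the outcomes" are "not balanced by stratified randomization, we will adjust for these in the primary analyses". It names no predictor and does not say what counts as imbalance.

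No section names the patient's earlier quantity as a covariate. Section 7.3.1 names age, race/ethnicity and gender, for secondary analyses. Section 7.3.5 gives examples of provider, patient and practice variables, none of which is baseline quantity. Section 5.3 stratifies on clinic size and baseline prescribing rate, both above the patient level, and the plan does not say that either enters the model.

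Patients qualify for Stage 1 if they "have been prescribed at least 90 pills of benzodiazepine or sedative hypnotic in the prior 180 days" (Section 4.1). Stage 2 and the replication trial extend this to anticholinergics.

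**The concern.** A patient's past prescribed quantity is usually among the best available predictors of the future quantity. If it is left out, differences between patients in usual quantity stay in the error term. Stratifying providers on baseline rates does not remove that spread between patients.

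The conditional clause does not solve this, for two reasons. It acts only when imbalance is seen, so when the arms look balanced the precision is lost. And because it has no named covariate and no threshold, the choice of model is made after looking at the data. Two analysts following the text could report different main results.

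Precision matters most in Stage 2. Section 3.2.1 puts about half of some 200 providers in usual care, and Section 3.2.2 spreads those over up to five tools plus usual care: 100 / 6, or about 17 per arm. This count leaves out re-randomised Stage 1 intervention providers and any added anticholinergic prescribers.

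**Working it through.** **The plan's own figure.** There is none to reproduce. Section 7.2 covers the primary outcome and gives no SD, effect size or power for milligram equivalents.

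**Inputs.**
- ICC 0.3 and 20 patients per provider: Section 7.2, adaptive trial, primary outcome.
- ICC 0.1: Section 7.2, replication trial, primary outcome.
- Using these values for the secondary outcome is an assumption.
- The correlations between baseline and follow-up quantity, within providers (rw) and between providers (rb), are assumptions. The documents give none.

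**Formula.** The variance of the adjusted comparison relative to the unadjusted one, with m patients per provider, is

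F = [(1 − rw²)(1 − ICC) + m·ICC·(1 − rb²)] / [(1 − ICC) + m·ICC]

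If rw = rb = r, this reduces to 1 − r² at any ICC. The equivalent sample multiplier is 1/F. For a comparison that would have 80% power unadjusted (a reference point, not a claim about this trial), the adjusted power is Φ((1.960 + 0.842)/√F − 1.960).

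**Results.**

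| rw | rb | ICC, m | Calculation | F | Variance removed | 1/F | 80% power becomes |
|---|---|---|---|---|---|---|---|
| 0.5 | 0.5 | any | 1 − 0.25 | 0.75 | 25% | 1.33 | 90% |
| 0.7 | 0.7 | any | 1 − 0.49 | 0.51 | 49% | 1.96 | 97% |
| 0.6 | 0 | 0.1, 20 | (0.64 × 0.9 + 2.0) / (0.9 + 2.0) = 2.576 / 2.9 | 0.89 | 11% | 1.13 | 84% |
| 0.6 | 0 | 0.3, 20 | (0.64 × 0.7 + 6.0) / (0.7 + 6.0) = 6.448 / 6.7 | 0.96 | 4% | 1.04 | 81% |

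In the last two rows most of the variance lies between providers (2.0 of 2.9 units and 6.0 of 6.7), where the covariate is assumed to predict nothing.

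**Simulation check.** Quantities were lognormal with 5% or 30% zeros, ICC 0.1, about 15 patients per provider and 17 or 67 providers per arm, with 1,500 runs per setting. The model was Gaussian with identity link and cluster-robust standard errors. The shape, the zeros and the correlations are assumptions. With raw correlations of 0.37 to 0.72, the variance adjusted for raw baseline quantity was 0.40 to 0.77 of the unadjusted variance. These runs set the within- and between-provider correlations equal, so they do not test the low end of the table.

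Type I error at nominal 0.05:

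| Providers per arm | Unadjusted | Adjusted |
|---|---|---|
| 67 | 0.049-0.067 | 0.046-0.065 |
| 17 | 0.063-0.080 | 0.062-0.087 |

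The excess at 17 per arm appears with and without adjustment, so it goes with the small number of clusters.

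**Is the covariate obtainable?** Eligibility needs a pill count over 180 days, so the orders must be read. Milligram equivalents follow from those orders by the same conversion that the outcome needs. They are not listed as extracted: Section 6.1 names no patient-level quantity (its list is open), and the schedule in Section 3.8 marks prescribing only in follow-up columns. The value is therefore derivable, but nothing shows that it is already in hand.

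**The case against.** The strongest reply is that the unadjusted mean difference is unbiased under randomisation, that providers are stratified on baseline rates, and that Section 7.3.2 already provides for chance imbalance. All of this is true. It rules out a charge of bias, and it would be wrong to say that the plan never adjusts. It does not restore the precision lost when the arms look balanced, and it leaves the model choice open.

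A second reply is that the gain may be small. That stands: with prediction only within providers it is about 4-11%, and the documents cannot say where in the range the trial lies.

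Three stronger readings might be inferred and are not supported.

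- *Normal errors make the analysis invalid because the outcome is skewed.* The documents describe no distribution. An identity link still targets the difference in mean quantity, and with 67 providers per arm the assumed skew did little to type I error.
- *The open follow-up window in Stage 2 biases the comparison.* Section 3.2.2 sets at least 8 months and Section 3.6 about 8 months. A longer common window applies to every arm alike, so it changes the scale of the totals without favouring an arm. The replication trial is fixed at 12 months.
- *Clustering is ignored for this outcome.* Section 7.3.1b specifies generalized estimating equations for the replication trial. For the adaptive trial, Section 7.3.1a ties its mixed model to the primary outcome and Section 7.3.2 says only generalized linear models. That is a gap in wording.

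**Conclusion.** The point holds as one of efficiency and prespecification on a secondary outcome. The likely strongest predictor can be derived from data that the trial must read anyway, and the plan leaves its use to an undefined imbalance check. Adjustment would remove about 25-49% of the variance under equal within- and between-provider correlations of 0.5-0.7, and about 4-11% under the unfavourable clustered case. Every case examined shows some gain, but its size cannot be fixed from the documents. The estimates rest on assumed correlations and on ICC and cluster-size values stated for the primary outcome. The planned estimate is not biased.

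**What to change.** In Section 7.3.2:

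1. Name each patient's milligram equivalents in the 180 days before randomisation as a covariate in the main analysis of this outcome. State that the window ends at randomisation, because the patient criterion gives no reference date for its 180 days.
2. Add the stratification factors, clinic size and baseline prescribing rate. Sections 3.2.2 and 3.2.3 describe a different set from Section 5.3, so list those actually used.
3. Delete the imbalance trigger for this outcome and report the unadjusted result as a sensitivity analysis.
4. State that the model accounts for clustering by provider, with a small-sample correction where there are few providers per arm.

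The cost is SAP wording plus a derivation of baseline milligram equivalents using the outcome's own conversion. The target, a difference in mean cumulative quantity, does not change. Adjustment alone does not correct the few-cluster excess in type I error, which is why item 4 is needed.
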